3. PATIENT SELECTION

3.1 Eligibility Criteria

3.1.1 Patients must have:

- A histologically confirmed diagnosis of CLL/SLL/B-cell PLL according to the International Workshop on CLL/SLL/B-cell PLL or variant of these [IWCLL¹⁴ or World Health Organization (WHO) Criteria] and meet criteria for treatment or have need for cytoreduction for stem cell transplantation or alternative cell therapy.

OR

A histologically confirmed diagnosis of mantle cell lymphoma (MCL) or diffuse large B-cell lymphoma (DLBCL) de novo or in the setting of transformation from an indolent lymphoma (including DLBCL not otherwise specified) according to the World Health Organization criteria for diagnosis of NHL.

AND

- Patients must have received at least one prior therapy for CLL or NHL, need additional treatment (or have need for cytoreduction as mentioned above), and meet criteria for relapsed or refractory disease. They may not be a candidate for curative therapy. **Relapsed disease** is defined as a patient who previously achieved a CR or a PR, but after a period of six or more months demonstrates evidence of disease progression. **Refractory disease** is defined as progression within six months of the last anti-leukemic or anti-lymphoma therapy, or any response less than a CR or PR.

EXCEPT

- Patients in Cohort 3 (selinexor added to ibrutinib for patients receiving frontline therapy) must be receiving ibrutinib as their initial therapy for CLL or SLL. These patients must have been receiving ibrutinib for at least 1 year before enrollment

3.1.2 Patients must be ≥ 18 years of age.

3.1.3 Patients must have an Eastern Cooperative Oncology Group (ECOG) performance status of < 2 . (See Appendix A.)

3.1.4 Patients with NHL must have objective, documented evidence of disease prior to study entry.

3.1.5 Patients must have normal organ function defined as:

- Platelet count $\geq 50,000/\text{mm}^3$ in the absence of bone marrow involvement; patients with bone marrow involvement only require a platelet count of $\geq 30,000/\text{mm}^3$
- Absolute neutrophil count $\geq 1000/\text{mm}^3$ in the absence of bone marrow involvement; patients with bone marrow involvement are not required to have a minimum absolute neutrophil count
- Creatinine clearance [as calculated by Cockcroft Gault equation= $(140-\text{age}) * \text{Mass (kg)} * (0.85 \text{ if female}) / (72 * \text{creatinine mg/dL}) \geq 30\text{mL/min}$]
- AST/ALT < 2.5 times upper limit of normal (ULN)

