11.1.3 Response Criteria for CLL Patients

Definition of Response for CLL Patients: Criteria for response will utilize the IWCLL Response criteria¹⁴.

Complete response (CR):

CR requires all of the following criteria as assessed at least 2 months after completion of therapy:

- Peripheral blood lymphocytes (evaluated by blood and differential count) below $4 \times 10^9/L$ ($4000/\mu L$). The presence of minimal residual disease (MRD) after therapy should be assessed. The sensitivity of the method used to evaluate for MRD should be reported.
- Absence of significant lymphadenopathy (e.g., lymph nodes > 1.5 cm in diameter) by CT scan of the abdomen, pelvis, and thorax.
- No hepatomegaly or splenomegaly by physical examination.
- Absence of constitutional symptoms.
- Blood counts above the following values:
 - Neutrophils more than $1.5 \times 10^9/L$ ($1500/\mu L$) without need for exogenous growth factors.
 - Platelets more than $100 \times 10^9/L$ ($100\,000/\mu L$).
 - Hemoglobin more than 110 g/L (11.0 g/dL) without red blood cell transfusion or need for exogenous erythropoietin.
- A marrow aspirate and biopsy should be performed at least 2 months after the last treatment and if clinical and laboratory results as above demonstrate that a CR has been achieved.
 - To define a CR, the marrow sample must normocellular for age, with less than 30% of nucleated cells being lymphocytes. Lymphoid nodules should be absent. If lymphoid nodules are present then these nodules should be recorded as nodular PR. However, immunohistochemistry should be performed to define whether these nodules are composed primarily of T cells or lymphocytes other than CLL cells or of CLL cells. If the marrow is hypocellular, a repeat determination should be performed after 4 weeks, or until peripheral blood counts have recovered. However, this time interval should not exceed 6 months after the last treatment. A marrow biopsy should be compared with that of pretreatment marrow. The quality of the CR should be assessed for MRD by flow cytometry or by immunohistochemistry (IHC).

CR with incomplete marrow recovery (CRi):

All the criteria for a CR (including the marrow examination) have been met though there is persistent anemia or thrombocytopenia or neutropenia apparently unrelated to CLL but related to drug toxicity.

Partial response (PR) PR is defined as follows:

- A decrease in the number of blood lymphocytes by 50% or more from the value before therapy.

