- Reduction in lymph node size by 50% or more either in the sum products of up to 6 lymph nodes, or in the largest diameter of the enlarged lymph node(s) detected prior to therapy.
- No increase in any lymph node, and no new enlarged lymph node. In small lymph nodes (< 2 cm), an increase of less than 25% is not considered to be significant.
- A reduction in the noted pretreatment enlargement of the spleen or liver by 50% or more, as detected by CT scan.
- The blood count should show one of the following results:
- Neutrophils more than $1.5 \times 10^9/L$ ($1500/\mu L$) without need for exogenous growth factors.
- Platelet counts greater than $100 \times 10^9/L$ ($100\,000/\mu L$) or 50% improvement over baseline.
- Hemoglobin greater than 110 g/L (11.0 g/dL) or 50% improvement over baseline without requiring red blood cell transfusions or exogenous erythropoietin.

Progressive Disease:

Characterized by at least one of the following:

- Appearance of any new lesion, such as enlarged lymph nodes (>1.5 cm), splenomegaly, hepatomegaly, or other organ infiltrates.
- An increase by 50% or more in greatest determined diameter of any previous site.
- An increase in the previously noted enlargement of the liver or spleen by 50% or more or the de novo appearance of hepatomegaly or splenomegaly.
- An increase in the number of blood lymphocytes by 50% or more with at least 5000 B-lymphocytes per microliter.
- Transformation to a more aggressive histology (e.g., Richter syndrome). Whenever possible, this diagnosis should be established by lymph node biopsy.
- Occurrence of cytopenia (neutropenia, anemia, or thrombocytopenia) attributable to CLL. During therapy, cytopenias cannot be used to define disease progression.
- The progression of any cytopenia (unrelated to autoimmune cytopenia), as documented by a decrease of Hb levels by more than 20 g/L (2 g/dL) or to less than 100 g/L (10 g/dL), or by a decrease of platelet counts by more than 50% or to less than $100 \times 10^9/L$ ($100\,000/\mu L$), which occurs at least 3 months after treatment, defines disease progression, if the marrow biopsy demonstrates an infiltrate of clonal CLL cells.

Stable Disease:

Patients who do not fulfill the criteria for complete or partial response as defined above but do not exhibit progressive disease will be considered as having stable disease.

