13.5 Definition of Secondary Endpoints

13.5.1 Toxicity will be graded by CTCAEv4.0. A copy of the CTCAE version 4.0 can be downloaded from the CTEP web site
http://ctep.cancer.gov/protocolDevelopment/electronic_applications/ctc.htm.

13.5.2 Clinical response and survival will be measured by:

- International Working Group Criteria for NHL patients.
- IWCLL 2008 Guidelines for CLL patients.

Response criteria are detailed in Section 10.

Responders will be defined as those with complete response (CR) or partial response (PR). Overall response rate (ORR) will be calculated as the number of evaluable responders divided by the total number of evaluable patients and will be analyzed by cohort. All patients who receive at least one dose of study medication will be included in the ORR and progression free survival.

Progression Free Survival (PFS): PFS will be calculated from the date of study enrollment to disease progression or death, whichever occurs first. Patients who do not progress or die will be censored at the time of last contact with response assessment by physical exam and laboratory studies.

Overall Survival (OS): OS will be calculated from the date of study enrollment to death. Patients who do not die will be censored at the time of last contact. This will be analyzed in each cohort independently.

13.5.3 Response as related to chronic lymphocytic leukemia (CLL) karyotype and IgVH mutational status. Response criteria are detailed in Section 10.

13.5.4 For Cohort 3, the rate of deepening of response is defined as the percentage of patients who attain a MRD negative complete response (MRD- CR) at the end of 14 cycles of selinexor plus ibrutinib.

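### The CLL partial-response rule requires lymphocytes to halve even when the entry count is below the CR limit, so a clear nodal response can be scored stable disease and ORR can be understated

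*Combined protocol and SAP*

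**What the plan says.** Section 11.1.3 lists the PR criteria for CLL. The lymphocyte item is "A decrease in the number of blood lymphocytes by 50% or more from the value before therapy", with no condition on the starting value. The organ item is "A reduction in the noted pretreatment enlargement of the spleen or liver by 50% or more, as detected by CT scan", and the node item likewise refers to nodes found before therapy. For the marrow lineages the list is lenient: "The blood count should show one of the following results", followed by neutrophils, platelets and hemoglobin.

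The CR lymphocyte item is an absolute limit: "Peripheral blood lymphocytes (evaluated by blood and differential count) below" 4 × 10^9/L. CR also requires no significant lymphadenopathy, with 1.5 cm as the example.

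CRi is defined as follows: "All the criteria for a CR (including the marrow examination) have been met though there is persistent anemia or thrombocytopenia or neutropenia", where the cytopenia comes from drug toxicity rather than CLL. Stable disease (SD) is the residual class: "Patients who do not fulfill the criteria for complete or partial response as defined above but do not exhibit progressive disease".

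Section 13.5.2 then states: "Responders will be defined as those with complete response (CR) or partial response (PR". CRi is not named. Section 13.8.2 reports ORR at the MTD with an exact 95% confidence interval.

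On eligibility, Section 3.1.1 admits patients with "A histologically confirmed diagnosis of CLL/SLL/B-cell PLL". Section 3.1.5 sets no minimum lymphocyte count, and Section 3.2.2 lets patients already on ibrutinib stay on it. Sections 11.1 and 13.5.2 assign criteria to CLL and NHL patients only and do not mention SLL.

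**The concern.** On the lymphocyte item, the lower response category is harder to reach than the higher one when the entry count is normal or only slightly raised. A patient whose disease is mainly nodal may have little lymphocytosis to lose. If that patient's nodes shrink well but do not clear, CR fails on node size and PR fails on a count that was never raised. The residual SD rule then applies.

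ORR is a secondary endpoint in a small group. The misclassification runs in one direction only, and the reported confidence interval does not reflect it. ORR would then depend partly on how many enrolled patients started with low counts rather than on drug activity.

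**Working it through.** **Where the two lymphocyte items conflict.** PR needs a count at or below half the entry value; CR needs a count below 4 × 10^9/L. Half of 8 is 4, so any patient who entered at 8 × 10^9/L or more and is now below 4 has also met the PR item. Below an entry count of 8, the PR item can be the stricter one. Below 4, the patient already meets the CR limit before treatment and must still halve the count for PR.

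**Patient A (normal entry count, PR-quality nodes).** Lymphocytes go from 2.0 to 1.6 × 10^9/L; nodes shrink 75% and the largest is still 2.0 cm.
- CR: 1.6 < 4, so the lymphocyte item is met. The 2.0 cm node exceeds 1.5 cm, so CR fails.
- PR: the nodal reduction (75%) exceeds 50%. The lymphocyte change is (1.6 − 2.0)/2.0 = −20% against the required −50%, so PR fails.
- With no progression, the result is SD.

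**Patient B (CRi with clearly raised lymphocytes at entry).** The count is now below 4, nodes have cleared and the marrow meets CR. PR requires only one adequate lineage. With one or two drug-related cytopenias, this patient normally meets PR and counts in ORR whether or not CRi is listed. A responder is lost on this limb alone only if all three lineages fail.

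**Patient C (both gaps together).** Normal entry count, nodes and marrow cleared, one drug-related cytopenia, lymphocytes not halved. This is CRi, and it fails PR on lymphocytes. If CRi is not read as CR, the result is SD.

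**Effect of one reclassification.** Sections 13.1 and 13.7 plan up to 10 CLL patients in the MTD expansion. Taking n = 10, exact (Clopper-Pearson) 95% intervals are:
- 7/10 = 70%: 34.8 to 93.3.
- 8/10 = 80%: 44.4 to 97.5.

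**Illustrative range.** The documents give no share of patients with low entry counts, so these shares are assumptions. Scored ORR = true ORR × (1 − share of responders that the rule cannot score).
- True ORR 60% (assumed): share 10% gives 0.60 × 0.90 = 54%; share 30% gives 0.60 × 0.70 = 42%.
- True ORR 71% (the ibrutinib figure cited in Section 2.3): shares 5%, 10%, 20% and 30% give 67%, 64%, 57% and 50%.

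Both sets are worst cases. They apply the loss to all responders although Patient A's problem does not affect complete responders, and they assume that no low-count patient halves the count. Some would: 3.8 to 1.8 is a fall of 2.0/3.8 = 53%.

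**Cohort 3.** Section 13.2 gives the probability of at least 3 MRD-CR in 10 patients. The exact binomial reproduces its table: 0.070, 0.322, 0.474, 0.617, 0.738 and 0.833 at true rates 0.1, 0.2, 0.25, 0.3, 0.35 and 0.4. The plan does not say whether MRD-negative CRi counts. If it does not, and 10%, 20%, 30% or 50% of MRD-negative complete responders were CRi (assumed), the effective rate at a true 30% is 0.27, 0.24, 0.21 or 0.15. The chance of passing then falls from 0.617 to 0.534, 0.444, 0.353 or 0.180.

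**The case against.** The strongest reply is that Sections 11.1.3 and 13.5.2 adopt the IWCLL criteria by reference, and the source may put a condition on the lymphocyte item. That cannot be checked from these documents. It would not clearly settle the matter either: Section 11.1.3 sets out its own list, SD is judged against the criteria as set out there, and nothing says which text governs.

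Second, scoring SLL on the CLL list is an inference. Eligibility and objectives group SLL with CLL, but the response sections do not assign it. This stands, so the point is conditional for SLL. It does not depend on SLL alone, because CLL patients can also enrol with low counts, for example while already on ibrutinib.

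Third, a reader might infer that leaving CRi out of Section 13.5.2 turns CRi patients into SD. The documents do not support that. The category is named as a form of CR and can be read as one, and most CRi patients meet PR through the one-lineage rule in any case. CR is also assessed at least two months after therapy ends, so drug-related failure of all three lineages would have to persist until then.

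Fourth, ORR is descriptive, with no threshold, test or power attached. One reclassified patient lies well within the interval at n = 10. This limits the consequence but does not justify a rule that misscores Patient A.

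**Conclusion.** The point holds in a limited form. Read as written, the PR list can score a clear nodal partial response as SD when the entry count is below 4 × 10^9/L, and ORR can be understated as a result. For SLL this assumes that SLL is scored on this list.

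A reader might go further and conclude that ORR is understated, or that a true 60% would read as 54% to 42%. The documents support neither. They give no share of low-count patients, and that range is a worst case on assumed shares. What can be said is that each misclassified patient moves a 10-patient ORR by 10 points, always downward.

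The effect of the CRi omission on ORR is small: it loses a responder only when all three lineages fail or the lymphocyte item fails as well. Its more material consequence is the unanswered question of what counts as MRD-CR in Cohort 3, whose size again rests on an assumed CRi share. No stated sample size or error rate for ORR changes, because none is stated.

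**What to change.** In Section 11.1.3, reword the PR lymphocyte criterion as a decrease of 50% or more from the pre-treatment value, or a count below 4 × 10^9/L. The either/or form is better than waiving the item only for entry counts below 4. Under a waiver, a patient going from 5.0 to 3.0 (−40%) with a 75% nodal reduction would still be SD, while one entering at 3.9 would need no fall. State in the same section that SLL is scored on this list.

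In Section 13.5.2, define CLL responders as CR, CRi or PR, including nodular PR, and state whether MRD-negative CRi counts as MRD-CR for the Cohort 3 rule.

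The cost is a few sentences of protocol wording. Blood counts, imaging and marrow examinations are already in the study calendars, so no new data are needed.

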- With the exception of splenic and hepatic nodules, involvement of other organs is usually assessable and no measurable disease should be present.
- Bone marrow assessment is irrelevant for determination of a PR if the sample was positive before treatment. However, if positive, the cell type should be specified (e.g., large-cell lymphoma or small neoplastic B cells). Patients who achieve a CR by the above criteria, but who have persistent morphologic bone marrow involvement, will be considered partial responders. When the bone marrow was involved before therapy and a clinical CR was achieved, but with no bone marrow assessment after treatment, patients should be considered partial responders.
- No new sites of disease should be observed.
- If performed, the post-treatment PET should be positive in at least one previously involved site.

Stable Disease (SD):

Patient fails to attain the criteria needed for a CR or PR, but does not fulfill those for progressive disease (see below). If performed, the PET should be positive at prior sites of disease, with no new areas of involvement on the post-treatment CT or PET.

Progression (PD) or Relapse:

- Lymph nodes should be considered abnormal if the long axis is > 1.5 cm, regardless of the short axis. If a lymph node has a long axis of 1.1 to 1.5 cm, it should only be considered abnormal if its short axis is > 1.0 . Lymph nodes ≤ 1.0 by ≤ 1.0 will not be considered as abnormal for relapse or progressive disease.
- Appearance of any new lesion > 1.5 cm in any axis during or at the end of therapy, even if other lesions are decreasing in size. Increased FDG uptake in a previously unaffected site should only be considered relapsed or progressive disease after confirmation with other modalities. In patients with no prior history of pulmonary lymphoma, new lung nodules identified by CT are mostly benign. Thus, a therapeutic decision should not be made solely on the basis of the PET without histologic confirmation.
- At least a 50% increase from nadir in the SPD of any previously involved nodes, or in a single involved node, or the size of other lesions (e.g., splenic or hepatic nodules). To be considered progressive disease, a lymph node with a diameter of the short axis of $<$

1.0 cm must increase by $\geq 50\%$ and to a size of 1.5 x 1.5 cm, or > 1.5 cm in the long axis.

- At least a 50% increase in the longest diameter of any single previously identified node > 1.0 cm in its short axis.

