11.1.4 Duration of Response

Duration of overall response: The duration of overall response is measured from the time measurement criteria are met for CR or PR (whichever is first recorded) until the first date that recurrent or progressive disease is objectively documented.

The duration of overall CR is measured from the time measurement criteria are first met for CR until the first date that progressive disease is objectively documented.

Duration of stable disease: Stable disease is measured from the start of the treatment until the criteria for progression are met, taking as reference the smallest measurements recorded since the treatment started, including the baseline measurements.

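### The CLL nodal progression rule has no minimum end size, so a small residual node can count as progression while still meeting the CR node rule

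*Combined protocol and SAP*

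**What the plan says.** Section 11.1.3 lists the CLL progression criteria, any one of which is enough. The nodal criterion for existing disease is "An increase by 50% or more in greatest determined diameter of any previous site". It gives no minimum size and names no reference scan.

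Other rules bear on the same measurement:

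- **CLL new lesions (11.1.3, Progressive Disease):** "Appearance of any new lesion, such as enlarged lymph nodes (>1.5 cm", so a size floor applies to new nodes.
- **CLL complete response (11.1.3):** "Absence of significant lymphadenopathy (e.g., lymph nodes > 1.5 cm in diameter) by CT scan of the abdomen, pelvis, and thorax".
- **CLL partial response (11.1.3):** "In small lymph nodes (< 2 cm), an increase of less than 25% is not considered to be significant". This tolerance sits in the PR rule and stops at 25%, so it does not reach a 50% change.
- **Duration of stable disease (11.1.4):** progression is judged "taking as reference the smallest measurements recorded since the treatment started", baseline included. The neighbouring sentences on duration of response do not repeat this, and neither does the PFS definition in 11.1.5.

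Section 11.1.3 also says that the cited IWCLL criteria are used. PFS is a secondary endpoint (13.5.2), described by Kaplan-Meier curves for patients treated at the MTD (13.8.2). The primary endpoint is DLT (13.4).

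**The concern.** A purely relative rule becomes more sensitive in absolute terms as the node gets smaller. For a node of 1.0 cm or less, a 50% increase is at most 5 mm and leaves the node at or below 1.5 cm, the size above which the same section begins to call a CLL node significant or enlarged. One measurement can then satisfy the CR node rule and a progression criterion together. An old node regrowing to 12 mm is progression, whereas a new 12 mm node is not an enlarged node.

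The patients most exposed are those whose nodes shrank most. A false call sets the PFS event date and ends the duration of response. Section 5.19 also lists progression among the events that end treatment, although Section 5.21 leaves removal to the investigator's discretion.

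**Working it through.** The plan gives no event count, power or error rate for PFS, so there is no figure of its own to reproduce. The check has three steps.

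**1. The rules applied to the same node.** As written, progression is reached at 1.5 × the reference diameter.

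| Smallest diameter | +50% | Absolute change | Nodal PD as written | Above 1.5 cm |
|---|---|---|---|---|
| 6 mm | 9 mm | 3 mm | yes | no |
| 8 mm | 12 mm | 4 mm | yes | no |
| 10 mm | 15 mm | 5 mm | yes | no |
| 11 mm | 16.5 mm | 5.5 mm | yes | yes |

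The conflict is confined to nodes whose smallest diameter is 10 mm or less. It follows from the protocol's own 50% and 1.5 cm thresholds, without any outside figure.

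**2. Noise in one pair of scans.** Assume no true change and independent normal measurement error with standard deviation s. The SD is an assumption; the documents give none. For true diameter d,

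P(second ≥ 1.5 × first) = 1 − Φ(0.5d / (s√(1 + 1.5²))) = 1 − Φ(0.5d / (s√3.25)).

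For d = 8 mm and s = 1.0 mm this is 1 − Φ(4/1.803) = 1 − Φ(2.22) = 1.3%.

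| d | s = 1.0 mm | s = 1.5 mm | s = 2.0 mm |
|---|---|---|---|
| 6 mm | 4.80% | 13.36% | 20.27% |
| 8 mm | 1.33% | 6.95% | 13.36% |
| 10 mm | 0.28% | 3.22% | 8.28% |
| 20 mm | <0.01% | 0.01% | 0.28% |

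**3. Noise over repeated scans.** The setting is stable nodes, six scans while the node is already small, the running minimum as reference, and a call if any node reaches 1.5 × its minimum. This was simulated. Six matches the number of scans from pre-study through the first year in the dose-escalation and expansion calendar (pre-study, C2, C4, C7, C10, C13). A node that is still shrinking has fewer scans at its small size in that year. The number of nodes followed is also an assumption.

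| d | One node, s = 1.0 | Four nodes, s = 1.0 | Four nodes, s = 1.5 |
|---|---|---|---|
| 6 mm | about 36–37% | 84% | 99% |
| 8 mm | 13% | 43% | 92% |
| 10 mm | 3% | 12% | 72% |
| 12 mm | 0.6% | 2% | 42–43% |

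The columns agree with each other: at 8 mm, 1 − (1 − 0.13)⁴ = 1 − 0.573 = 43%. One 8 mm node at s = 1.5 mm gives 47%.

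Adding an end size above 15 mm cuts the four-node figures to 0.7% or less for nodes up to 10 mm. At 12 mm they become 0.3% (s = 1.0) or 14–15% (s = 1.5).

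**The case against.** Several points on the other side are sound, and they set the limits of this finding.

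- **Reference scan.** A reader might infer that the protocol names no reference, so that real regrowth is missed: a node going 40, 10, 30 mm is −25% from baseline but +200% from the minimum. The documents do not support that. Section 11.1.4 names the smallest measurement since treatment began. What stands is that it does so only in the stable-disease sentence, and the CLL bullets do not point to it.
- **Opposite readings.** False progression in a shrunken node needs the smallest-measurement reference; missed regrowth needs the baseline reference. A node going 40, 8, 12 mm is 12/40 − 1 = −70% from baseline. Both harms cannot follow from one reading, and 11.1.4 points to the first.
- **The NHL rules as a template.** A reader might take 11.1.2 as holding both safeguards. The nadir wording, "At least a 50% increase from nadir in the SPD of any previously involved nodes", belongs to the SPD bullet. The NHL single-node diameter bullet states neither a nadir nor an end size; it requires a short axis above 1.0 cm. The 1.5 cm end size covers only nodes with a short axis below 1.0 cm. There is no single NHL rule to copy.
- **Any previous site.** This most naturally means an involved site, so ordinary never-enlarged nodes are outside the rule. Involved nodes that shrank to about 1 cm or less remain exposed.
- **IWCLL.** The cited criteria may supply a floor. Their text is not in the documents, so this cannot be judged. The printed bullet is what sites have in front of them, and it has none.
- **Assumed inputs.** The percentages depend on the SD, the number of nodes, independent errors and mechanical calling. They illustrate sensitivity and do not estimate this trial's error rate.

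**Conclusion.** The missing size floor is a real inconsistency within 11.1.3: for nodes with a smallest diameter of 10 mm or less, the nodal progression bullet can be met by a node that the CR rule accepts and the new-lesion rule would not call enlarged. The result can be false or early progression dates, mainly in good nodal responders. For a stable 8 mm node over six scans at an assumed SD of 1.0 mm, the chance of a false call is about 13% with one node and 43% with four; it rises with the SD and falls quickly with node size.

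It would go too far to infer that PFS is corrupted. PFS is secondary, untested and descriptive; DLT does not use this bullet, and the Cohort 3 MRD-negative CR count does not use it directly. The effect is a possible shift in CLL progression dates, and in duration of response wherever that is reported. The groups are small, though: with 10 CLL patients at risk, one false event lowers the Kaplan-Meier curve by 1/10, or 10 percentage points. The unstated reference is a lesser matter of cross-referencing.

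**What to change.** In the CLL progression list of 11.1.3:

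1. Add an explicit minimum end size to the nodal bullet. Reconcile it with the 1.5 cm threshold already used in the CLL CR and new-lesion rules, and check it against the cited IWCLL criteria before fixing the value.
2. Cross-refer the nodal and the liver/spleen bullets to the smallest-measurement reference in 11.1.4, so that it plainly governs PFS and duration of response as well as stable disease.

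The nodal bullet could read: an increase of 50% or more in the greatest diameter of a previously involved site, relative to the smallest measurement since the start of treatment (see 11.1.4), with the resulting diameter above the stated minimum.

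The cost is one sentence and a cross-reference. The downside is that true regrowth of a very small node is dated slightly later: with a floor of 1.5 cm, a node with a smallest measurement of 8 mm would be called above 15 mm instead of at 12 mm. Where the smallest measurement exceeds 10 mm the floor changes nothing, because 1.5 times that value is already above 15 mm.
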